3.2.3 Study Interruption or Study Withdrawal

A patient may be taken off this study early or may discontinue participation in this clinical study due to the following factors:

- Serious or intolerable adverse reaction to treatment
- Progression of disease
- Protocol violation
- Withdrawal of consent
- Withdrawal of sponsor support

There is no limit to how long a patient can have their treatment on hold. Prolonged holds are not considered “serious or intolerable adverse reactions to treatment.”

3.2.4 Monitoring of everolimus suspected toxicities: Patients whose treatment is interrupted or permanently discontinued due to an adverse event or abnormal laboratory value suspected to be related to everolimus must be followed at least weekly until the adverse event or abnormal laboratory completely resolves or returns to baseline as clinically appropriate. For patients whose treatment is on hold, labs will be monitored every two weeks while on hold.

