3.2.5 Known Undesirable Side Effects of everolimus

Overall, safety data available from completed, controlled and uncontrolled studies indicate that everolimus is generally well tolerated at weekly or daily dose schedules. The safety profile is characterized by manageable adverse events (AEs). These AEs are generally reversible and non-cumulative.

Adverse events most frequently observed with everolimus are stomatitis, rash, diarrhea, fatigue, infections, asthenia, nausea, peripheral edema, decreased appetite, headache, dysgeusia, epistaxis, mucosal inflammation, pneumonitis, weight decreased, vomiting, pruritus, cough, dyspnea, dry skin, nail disorder, and pyrexia. Overall, the most frequently observed laboratory abnormalities include decreased hematologic parameters including hemoglobin, lymphocytes, platelets, and neutrophils (or collectively as pancytopenia); increased clinical chemistry parameters including cholesterol, triglycerides, glucose, aspartate transaminases, creatinine, alanine transaminases, and bilirubin; and decreased clinical chemistry parameters including phosphate and potassium. The majority of these AEs have been of mild to moderate severity (NCI CTC grade 1-2).

Everolimus has immunosuppressive properties and may predispose patients to bacterial, fungal, viral or protozoan infections, including infections with opportunistic pathogens. Localized and systemic infections, including pneumonia, other bacterial infections, invasive fungal infections, such as aspergillosis or candidiasis and viral infections including reactivation of hepatitis B virus, have been described in patients taking everolimus. Some of these infections have been severe (e.g. leading to sepsis, respiratory or hepatic failure) and occasionally have had a fatal outcome.

Physicians and patients should be aware of the increased risk of infection with everolimus. Treat pre-existing infections prior to starting treatment with everolimus. While taking everolimus, be vigilant for symptoms and signs of infection; if a diagnosis of infection is made, institute appropriate treatment promptly and consider interruption or discontinuation of everolimus. If a diagnosis of invasive systemic fungal infection is made, discontinue everolimus and treat with appropriate antifungal therapy.

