6.0 Statistical Considerations

This is a study of maintenance rituximab with mTor inhibition (everolimus) after high-dose consolidative therapy in CD20+, B-cell Lymphomas and Hodgkin's Lymphoma. It is hypothesized that the addition of new agents in patients with minimal residual disease will improve event free survival and that everolimus may act synergistically with rituximab.

Primary Objective:

To determine the safety of maintenance rituximab and prolonged mTOR inhibition with everolimus in CD20+, B cell lymphoma and Hodgkin's Lymphoma after high-dose consolidative therapy.

Secondary Objectives:

1. The secondary endpoint of this study is to evaluate event-free survival (EFS) at three years. EFS is defined as the interval from registration to the date of first objective disease progression, death from any cause, or last patient evaluation. Patients who have not progressed or died will be censored at the last date they were assessed and deemed relapse-free.
2. To determine whether maintenance rituximab with everolimus treatment reduces the frequency circulating cancer cells.
3. To determine if relapsed disease is sensitive, in-vivo, to mTor kinase inhibition.

Study Design:

Treatment will consist of rituximab 375mg/m² q 90 days (4 infusions) with everolimus 2.5 mg orally daily for one year. There will be no drug escalation in this study however serum drug levels will be monitored and the level of everolimus will be maintained in the therapeutic window. For patients outside the range of 3 – 15ng/mL and not experiencing grade 3 or higher toxicity, the dose will either be increased or decreased by 2.5mg per day to bring patients within range, down to 2.5 mg every 4 days. Addendum 4 provides details on dose adjustments and treatment holds. For patients experiencing grade 3 or higher toxicities adjustments will be made as detailed in addendum 4. The study will be monitored continuously for safety.

Sample size/Accrual Rate:

The accrual rate for this study is expected to be 20 patients per year. The safety objective of this trial is based on the precision of estimating grade 3 or higher toxicities. Sixty patients will allow us to estimate the proportion of patients experiencing grade 3 or higher toxicities with a precision of $\pm 13\%$.

Early Stopping Guideline for Safety:

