Reference: Internal Clinical Pharmacology Drug-drug interaction (DDI) memo, updated Oct. 2, 2011, 29-Oct-2012 which summarizes DDI data from three sources including the FDA's "Guidance for Industry, Drug Interaction Studies", the University of Washington's Drug Interaction Database, and Indiana University School of Medicine's Drug Interaction Table.

Addendum 4: Dose Modifications for abnormal serum drug concentrations without grade III/IV toxicities, grade \geq III toxicities (CTCAE version 4.0) except for stomatitis and lipid/hyperglycemia toxicities

- Patient will have regularly scheduled everolimus levels drawn throughout the study
- Everolimus is available in 2.5mg, 5mg and 10mg strengths
- The reference range for patients experiencing a <II common toxicity (CTCAE version 4.0) is 3-15ng/mL
- Anytime a dose is adjusted, repeat everolimus serum trough levels will be re-drawn 14 days (\pm 3 days) later. As clinically possible, all patients' other labs will be reset to match this new everolimus serum trough level schedule.
- Once everolimus is held due to high serum trough levels, everolimus should be held for 7 days before restarting at a lower dose level.
- During a treatment hold, everolimus levels will not be drawn once the serum trough level is less than 1.0.
- There is no limit on how long a patient can be on everolimus treatment hold. Labs will be monitored every two weeks while the patient is on hold.
- For patients >15 ng/mL or <3.0 ng/mL and not experiencing >II grade common toxicity, their dose will be adjusted by $+/-.2.5$ mg/day; lowest dose allowed is 2.5mg every 4 days. The study nurse will provide a calendar to patients when the dose level is 2.5 mg taken every 3 or 4 days
- If a patient on a schedule of 2.5 mg (QOD) or lower misses a dose, that dose should be made up.
- Non-hematologic grade \geq III CTCAE toxicities: hold drug until CTCAE toxicity is (I) but can be continued at grade 2 if the baseline values were within the range of grade 2 and restart at a dose level -2.5mg/day. Lowest dose allowed is 2.5mg every 4 days
- Grade 4 or 4 clinical failure – discontinue RAD001
- Recurrence of grade 4 toxicity after dose reduction – discontinue RAD001
- Hematologic grade \geq III CTCAE toxicity
 - Anemia
 - Hgb <8.0 g/dL: transfuse RBC; hold drug for 7 days or until Hgb >10 mg/dL (untransfused): whichever is longer. Restart at a dose - 2.5mg/day. Lowest dose allowed is 2.5mg every 4 days
 - Thrombocytopenia

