Patients with a clinical history of stomatitis/mucositis/mouth ulcers and those with gastrointestinal morbidity associated with mouth/dental infections, irritation of esophageal mucosa e.g. gastroesophageal reflux disease (GERD) and pre-existing stomatitis/mucositis must be monitored even more closely. Patients should be

instructed to report the first onset of buccal mucosa irritation/reddening to their study physician immediately.

Stomatitis/oral mucositis/mouth ulcers due to Everolimus should be treated using local supportive care. Please note that investigators in earlier trials have described the oral toxicities associated with Everolimus as mouth ulcers, rather than mucositis or stomatitis. If your examination reveals mouth ulcers rather than a more general inflammation of the mouth, please classify the adverse event as such. The suggested paradigm for treatment of stomatitis/oral mucositis/mouth ulcers is as follows:

1. For mild toxicity (Grade 1), use conservative measures such as non-alcoholic mouth wash or salt water (0.9%) mouth wash several times a day until resolution.
2. For more severe toxicity (Grade 2 in which case patients have pain but are able to maintain adequate oral alimentation, or Grade 3 in which case patients cannot maintain adequate oral alimentation), the suggested treatments are topical analgesic mouth treatments (i.e., local anesthetics such as benzocaine, butyl aminobenzoate, tetracaine hydrochloride, menthol, or phenol) with or without topical corticosteroids, such as triamcinolone oral paste 0.1% (Kenalog in Orabase®).
3. Agents containing hydrogen peroxide, iodine, and thyme derivatives may tend to worsen mouth ulcers. It is preferable to avoid these agents.
4. Antifungal agents must be avoided unless a fungal infection is diagnosed. In particular, systemic imidazole antifungal agents (ketoconazole, fluconazole, itraconazole, etc.) should be avoided in all patients due to their strong inhibition of everolimus metabolism, thereby leading to higher everolimus exposures. Therefore, topical antifungal agents are preferred if an infection is diagnosed. Similarly, antiviral agents such as acyclovir should be avoided unless a viral infection is diagnosed.

Addendum 6: Management of hyperlipidemia and hyperglycemia

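### For a grade 3 invasive systemic fungal infection above the lowest everolimus dose, Section 3.2.5 says discontinue while Addendum 4 says hold and restart lower, and no text says which governs

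*Combined protocol and SAP*

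**What the plan says.** Section 3.2.5, the account of everolimus side effects, gives two instructions on infection. For infection in general the physician should "institute appropriate treatment promptly and consider interruption or discontinuation of everolimus". For one kind of infection it is categorical: "If a diagnosis of invasive systemic fungal infection is made, discontinue everolimus and treat with appropriate antifungal therapy". That sentence is not tied to a CTCAE grade and mentions no resumption.

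Addendum 4 holds the dose-modification rules. For non-hematologic toxicity of grade III or higher the instruction is to "hold drug until CTCAE toxicity is (I) but can be continued at grade 2" where the baseline value was already grade 2, and then to restart 2.5 mg/day lower. Its heading excepts only stomatitis and the lipid and glucose toxicities. It also contains two grade 4 discontinuation lines, and it takes a patient off study if toxicity above grade II occurs at the lowest dose, 2.5 mg every 4 days.

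Three places send the reader to Addendum 4 for dose changes: Section 3.3.1, footnote 10 of the study calendar in Section 3.4.2, and Section 6, which says: "For patients experiencing grade 3 or higher toxicities adjustments will be made as detailed in addendum 4". None of them mentions the fungal-infection sentence in Section 3.2.5.

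**The concern.** Both texts can apply to the same event, and they lead to different places. Staff who adjust the dose from Addendum 4, as Sections 3.3.1 and 6 direct, would hold everolimus and later resume it. Staff who follow Section 3.2.5 would stop it. The drug is immunosuppressive, and Section 3.2.5 itself says that some infections on everolimus have been severe and occasionally fatal. What is at stake is whether a patient is re-exposed after such an infection, and whether two compliant readers would treat that patient alike.

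**Working it through.** No arithmetic is needed to establish the conflict, and the plan gives no figure to reproduce. The check compares the texts.

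**Step 1: does discontinue simply mean hold?** The sentence just before the fungal rule tells the physician to "consider interruption or discontinuation of everolimus", naming two different actions. Section 3.2.4 draws the same line: "Patients whose treatment is interrupted or permanently discontinued due to an adverse event". Permanence is therefore an inference from usage, not a stated word, but it is the natural reading.

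**Step 2: does a fungal infection fall under Addendum 4?** Section 3.2.5 lists infection among the drug's adverse events: "Adverse events most frequently observed with everolimus are stomatitis, rash, diarrhea, fatigue, infections". An infection scored grade 3 then meets the wording of the non-hematologic rule, and the heading does not except it. The documents do not say how an invasive fungal infection will be graded, so the grade is an assumption.

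**Step 3: compare the rules case by case.**

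| Invasive systemic fungal infection | Section 3.2.5 | Addendum 4 | Result |
|---|---|---|---|
| Grade 2 or lower | Discontinue | Toxicity hold not triggered | Only Section 3.2.5 speaks |
| Grade 3, above the lowest dose | Discontinue | Hold, then restart 2.5 mg/day lower | Contradiction |
| First grade 4 event, above the lowest dose | Discontinue | Lines point both ways | Unclear |
| Grade 4 recurring after a dose reduction | Discontinue | Discontinue | Agree |
| Grade 3 or higher at the lowest dose | Discontinue | Off study | No re-exposure under either |

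**Step 4: why a first grade 4 event is unclear.** One Addendum 4 line calls for discontinuation but is garbled: it gives the grade twice and refers to a clinical failure that it does not define. The next line discontinues when grade 4 toxicity returns once the dose has been lowered, which implies that a first grade 4 event may be followed by a restart. The general rule for grade III or higher also covers grade 4.

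**Step 5: is there a written order of precedence?** None was found. Section 3.2.5 calls Addenda 4 to 7 recommendations, whereas Sections 3.3.1 and 6 say that changes will follow Addendum 4. That difference in force does not decide between the two rules.

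**The case against.** The strongest reply is that a specific instruction should prevail over a general one. The Addendum 4 heading is plainly not a complete list of exceptions: non-infectious pneumonitis (Addendum 7) and hepatitis B reactivation (Addendum 9) have their own rules and are not named there. On that view the fungal sentence is one more event-specific rule, and a careful clinician would follow it. This reading is reasonable, and it lowers the chance that the conflict causes harm. But it is not written down. Pneumonitis and hepatitis B each have an addendum that Section 3.2.5 points to. The fungal rule is one sentence in a narrative, and none of the texts directing staff to Addendum 4 leads back to it.

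A reader might infer four stronger points. The documents do not support them.

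- **Addendum 4 orders a restart after every non-hematologic toxicity of grade III or higher.** It does not. It has grade 4 discontinuation lines and an off-study rule at the lowest dose, and other addenda cover particular events.
- **The rules also conflict for other grade 3 infections.** Being told to consider interruption is compatible with a mandatory hold, so a clinician who follows Addendum 4 satisfies both texts.
- **Patients would be restarted while on an interacting azole.** Addendum 5 says systemic imidazole antifungals "should be avoided in all patients due to their strong inhibition of everolimus metabolism", and Addendum 1 has its own rules for inhibitors. Those apply whichever infection rule governs. That a restarted patient would still be taking such a drug is conjecture.
- **Each affected patient moves a safety proportion by 1/60 = 1.7 percentage points.** Section 6 states its ±13% precision for the proportion with grade 3 or higher toxicity. In the conflict case the infection is already grade 3, so the patient counts under either rule and this event shifts nothing. In Section 6's other safety count, an unexpected admission is a failure under either rule.

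**Conclusion.** The contradiction is real but narrow. It is clear for an invasive systemic fungal infection scored grade 3 in a patient above 2.5 mg every 4 days. For a first grade 4 event the text is ambiguous rather than contradictory.

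This rests on three assumptions: such an infection would be scored grade 3 or higher, it would be handled as a toxicity under Addendum 4, and discontinue means something other than a temporary hold. The first is not addressed in the documents; the other two are supported by the wording of Sections 3.2.4 and 3.2.5.

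The documents give no expected frequency, so the number of patients affected cannot be stated. No sample size, power or error rate changes, and no shift in the primary safety analysis has been shown. The point matters because two readers who each comply with the protocol could give the same patient opposite treatment after a serious infection.

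**What to change.** Reconcile Section 3.2.5 with Addendum 4 so that one rule governs invasive systemic fungal infection. Either name this infection among the exceptions in the Addendum 4 heading with a pointer to Section 3.2.5, or align the wording of the two texts. State the resulting precedence where Sections 3.3.1 and 6 refer to Addendum 4, and carry it into the study calendar footnote that repeats the reference. Rewrite the garbled grade 4 line so that, together with the recurrence line, it is clear what follows a first grade 4 event. Which clinical rule applies is for the investigators to decide.

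The cost is a wording amendment, which under Section 4 goes to Novartis, the investigator and the IRB. It adds no patients, visits or procedures.

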3.3 Treatment

Pre-treatment evaluation (to be completed ≤ 30 days before treatment initiation)

History and Physical Examination

History should try to document the pre high dose consolidative therapy MIPI score (age at diagnosis, ECOG performance status, LDH and WBC) and FLIPI score (age of diagnosis, LDH, ECOG performance status, number of extranodal sites, Ann Arbor stage) for Mantle and follicular lymphoma patients, respectively.

A detailed assessment of Hepatitis B/C medical history and risk factors must be done for all patients at screening, with testing performed prior to the first dose of everolimus. Please see Addendum 8 for action to be taken for patients with a positive baseline hepatitis B result.

CBC with platelet and reticulocyte count

Complete metabolic panel, immunoglobulin panel (IGG, IGA, IGM), fasting triglycerides, glucose and total cholesterol (cholesterol and triglycerides can be measured on either the screening visit or the day 1 visit)

PET/CT scans. If PET/CT is not possible a CT of the chest/abdomen/pelvis is required.

Bone marrow aspirate and biopsy: if bone marrow was previously involved

HCG urine pregnancy test for women of child bearing potential

Treatment initiation: treatment is to begin between six (6) weeks and ten (10) weeks after high dose consolidative therapy

3.3.1 Everolimus administration

The initial dose of everolimus will be 2.5mg orally daily for a total of one year to maintain a target trough concentration between 3-15 ng/mL

Everolimus should be administered orally once daily, preferably in the morning, at the same time every day with or without food.

Everolimus tablets should be swallowed whole with a glass of water.

The tablets must not be chewed or crushed.

If vomiting occurs, no attempt should be made to replace the vomited dose

Everolimus will be provided by Novartis. Everolimus is formulated as tablets for oral administration of 2.5mg, 5mg, and 10mg strength.

Dose modification will occur as per Addendum 4.

Everolimus can still be administered per protocol even if Rituximab treatment is on hold.

3.3.2 Concomitant therapy

Rituximab will be administered concomitantly with everolimus as per the dose and schedule below. Instructions for administration of Bactrim and Valtrex for PCP prophylaxis and herpes prophylaxis treatment, respectively, are also listed.

Patients will be instructed not to take any additional medications (including over-the-counter products) during the course of the study without prior consultation with the investigator. At each visit, the patient will be asked about any new medications he/she is or has taken after the start of the study drug. Additional information about clinically relevant drug interactions can be found in Addendums 1-3.

All Concomitant medications/significant non-drug therapies taken \leq 30 days prior to the start and after start of study drug, including physical therapy and blood transfusions, should be recorded.

Rituximab administration

Dose and schedule: 375mg/m² day +1 and then every 90 days for 1 year (a total of 4 infusions)

Rituximab will not be given unless the patient's ANC is greater than 1.5.

Administration as per institutional standard, with infusions 90 days apart, regardless of the study date that it was given. For example, if Rituximab is given on day 95 instead of 90, the next infusion will be given on day 185, not 180.

Rituximab can still be administered per protocol even if Everolimus treatment is on hold.

It is not considered a protocol deviation if Rituximab is withheld due to Rituximab-induced cytopenias. There is no limit to the number of Rituximab doses that can be held. For example, some patients may not get any doses of Rituximab, or possibly only one dose, if their counts have a history of extreme sensitivity to Rituximab.

Primary antimicrobial prophylaxis

Bactrim SS PO qd or equivalent/suitable antimicrobial regimen for PCP prophylaxis during everolimus administration

Valtrex 500mg PO bid or acyclovir 400 mg PO tid for herpes prophylaxis in HSV/CMV positive individuals during everolimus administration

3.3.3 Treatment compliance:

Everolimus compliance will be monitored by serum blood analysis. Records of study medication used, dosages administered, and intervals between visits will be recorded during the study. Drug accountability will be noted and patients will be asked to return all unused study medication. Rituximab will be infused at the cancer center.

3.4 Visit schedule and assessments

3.4.1 Visit schedule: Examination and Laboratory evaluations

Physical examination: Complete lymphomatous physical examination every ninety (90) days for the first two (years), then every six (6) months for the third year.

CBC with platelet count every two (2) weeks for the first sixty (60) days then monthly for a total of one (1) year, then every 90 days for the next two (2) years.

Metabolic panel every two (2) weeks for the first sixty (60) days then monthly for a total of one (1) year

Imunoglobulin panel (IgG, IgA, IgM), fasting triglycerides and fasting cholesterol levels monthly for a total of one (1) year.

Patients will be scheduled for an IVIG infusion if their IgG level falls below 500 mg/dL.

Patients with an IgG serum level of <500mg/dL will either have supplemental Ig administration or changes in primary oral antimicrobial prophylaxis per PI discretion.

HCG urine pregnancy testing every 4 weeks during everolimus administration and for 8 weeks post everolimus administration for women of child bearing potential

Everolimus serum trough levels every two (2) weeks for the first sixty (60) days then monthly for a total of one (1) year. Everolimus levels will not be drawn during a hold once the level is less than 1.0.

Research peripheral blood labs (2 green top tubes) every ninety (90) days for a total of three (3) years.

Bone marrow evaluation at ninety (90) days and at the end of cycle 13 (or the 365 day appointment when patients move into the follow-up stage) at PI's discretion. If a bone marrow evaluation is performed, an additional 10 ml green top tube of aspirate will be drawn for research purposes.

Adverse events and concomitant medications will be monitored throughout the duration of the study.

Survival/disease status will be assessed at year 4 and year 5.

Radiographic evaluation

Computerized Tomography (CT) of chest/abdomen/pelvis and whole body Positron emission tomography (PET) scanning every ninety (90) days for two (2) years, then every six (6) months for the third year.

CT scans of the neck and other structures as determined by physical examination

